6. AIMS AND OBJECTIVES

6.1 Main Hypothesis

Robotic surgery for rectal cancer results in a milder stress response and similar or better functional outcomes when compared to the laparoscopic approach.

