6.2 Primary Objectives

- 1. Assessment of sexual, urological and bowel function in patients undergoing rectal cancer surgery
- 2. Analysing postoperative stress and immune response in blood samples

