9. SAMPLING

In our retrospective study we demonstrated IPSS and IIEF score differences of more than 5.0 points between the 2 groups (see preliminary data). Assuming a 3.75 IPSS score and 4.4 IIEF score difference and a 0.05 (two-sided) significance level, 35 patients will be required in each group to provide 80% power.

We also carried out simulated cumulative scores from the study-specific CRF based on the Likert-scale for independent validation of our initial analysis. Considering 80% power and a 0.05 (two-sided) significance level, a minimum of 36 patients were needed in each arm to demonstrate a minimum difference in the cumulative score of 1 between the groups. This sample size calculation was carried out using the "stats" module in R (ver. 3.4.2) using a two-sided independent means test.

We have considered a maximum of 10% loss to follow-up for the long-term functional outcomes in our population during sample size calculations and will thus seek to recruit a minimum of 80 patients into our study.

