13. DATA ANALYSIS

13.1 Description of Analysis of Populations

Subjects from each cohort will be analysed separately. The populations will be defined as per protocol analysis, e.g., patients who completed the treatment as was originally allocated will be included in the analysis, as well as eligible subjects with no minor or major protocol deviations. Descriptive statistics will be provided for all discrete variables in the form of rates and proportions with 95% confidence intervals. Continuous variables will be described by mean, standard deviation, median and range.

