13.2 Analysis of Endpoints

We will analyse summary statistics for each allocation group, including means and standard deviations for normally distributed data and medians and interquartile ranges for non-normally distributed data.

Student's t test will be used to analyse the differences between the two groups (L-TME vs. R-TME). The paired t test will be used to compare postoperative urogenital, bowel and sexual functions in both groups to the preoperative functions. Fisher's exact test will be used for categorical data (e.g., age, sex, tumour location, T and N stage, and radiation therapy). A P-value of 0.05 will be considered statistically significant.

The analysis of the differences between groups of blood cell counts or number of lymphocyte subsets, and clinic pathological variables will be performed using Chi-square tests, Kruskal–Wallis tests, and analysis of variance tests. A P-value of 0.05 will be considered statistically significant.

Analysis of the QLQ-C30 and QLQ-CR29 questionnaires will be performed in accordance with the EORTC guidelines. Time to definitive deterioration in quality of life, with the use of a 10-point minimal clinically important difference, will be analyzed with the use of the Kaplan–Meier method and the log-rank test. Descriptions (by visit) and graphs will be presented.

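### Section 13.2 brings pre-operative function in only through paired tests within each arm, and does not say that the comparative conclusion on function rests on the between-arm difference in change

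*Protocol*

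**What the plan says.** Section 6.1 states a comparative hypothesis: robotic surgery is expected to give "similar or better functional outcomes when compared to the laparoscopic approach". The first primary objective in section 6.2 is worded without a comparator: "Assessment of sexual, urological and bowel function in patients undergoing rectal cancer surgery".

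Section 13.1 opens with "Subjects from each cohort will be analysed separately". It goes on to define a per-protocol population and the descriptive statistics.

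Section 13.2 then plans two kinds of t test in consecutive sentences. The first is between arms: "Student's t test will be used to analyse the differences between the two groups (L-TME vs. R-TME"). It names no outcome, no visit and no role for the baseline value. The second is within arms, and is the only test sentence that names function: "The paired t test will be used to compare postoperative urogenital, bowel and sexual functions in both groups to the preoperative functions". The same paragraph sets the threshold: "A P-value of 0.05 will be considered statistically significant".

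Section 9 sizes the study on a comparison between groups: "Assuming a 3.75 IPSS score and 4.4 IIEF score difference and a 0.05 (two-sided) significance level, 35 patients will be required in each group". A second calculation, described as a two-sided independent-means test, says that "a minimum of 36 patients were needed in each arm to demonstrate a minimum difference in the cumulative score of 1 between the groups".

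**The concern.** A P value from a before/after test in one arm says whether that arm changed. Setting it beside the other arm's P value does not show whether the two changes differ. One can fall below 0.05 and the other above it by chance when the true changes are identical.

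The hypothesis makes this more than a formality. Because it speaks of similar or better function, a significant decline after laparoscopic surgery next to a non-significant one after robotic surgery looks like support, with function apparently preserved in the robotic arm.

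Baseline is also central to this design. Section 5 criticises the earlier retrospective study at the same hospital because patients may not accurately recall their pre-operative function, and this study collects baseline function prospectively to remedy that. The arms are not randomised, so they may start from different levels. Yet section 13.2 explicitly uses baseline function only where it cannot answer the comparative question.

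**Working it through.** **Inputs.** From section 9: 36 per arm (35 in the IPSS/IIEF calculation), two-sided 0.05, 10% loss, 80 recruited. From section 7.2: six functional tools, four of them for one sex only, at 3, 6 and 12 months after surgery. Not in the protocol: the SD of change from baseline, and the expected decline.

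**The plan's own figure.** 36/(1 − 0.10) = 40 per arm, so 80 in total, which agrees with section 9. (35/(1 − 0.10) = 38.9, rounded up to 39 per arm, would give 78.)

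**What has to be assumed.** Let d be the true mean decline divided by the SD of change, the same in both arms. Because neither quantity is given, d is varied from 0 to 0.8.

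**Formula.** For a paired t test in n patients, p is the probability of a significant result in the direction of decline: p = P(T > t(0.975; n − 1)), with T noncentral t on n − 1 degrees of freedom and noncentrality d√n. The arms contain different patients and are independent, so

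- P(laparoscopic significant, robotic not) = p(1 − p);
- P(exactly one arm significant) = 2p(1 − p).

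The first is largest at p = 0.50, where it equals 0.50 × 0.50 = 0.25, whatever n is.

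**Results at n = 36 per arm** (√36 = 6, so d = 0.2 gives noncentrality 1.2)

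| d | p | p(1 − p) |
|---|---|---|
| 0 | 0.025 | 2.4% |
| 0.1 | 0.084 | 7.7% |
| 0.2 | 0.214 | 16.8% |
| 0.3 | 0.417 | 24.3% |
| 0.34 | 0.50 | 25.0% |
| 0.4 | 0.646 | 22.9% |
| 0.5 | 0.831 | 14.1% |
| 0.6 | 0.938 | 5.8% |
| 0.8 | 0.997 | 0.3% |

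**Sex-specific tools.** IPSS, IIEF, FSFI and the King's questionnaire have fewer than 36 per arm. At an assumed 20 per arm, p(1 − p) is 11.6% at d = 0.2, 23.9% at 0.4, 24.6% at 0.5 and 7.0% at 0.8, with the peak near d = 0.46. The peak moves to larger declines; its height does not change.

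**Comparison with a direct test.** In 100,000 simulated studies with n = 36 per arm and d = 0.34 in both, the laparoscopic-only pattern appeared in 25.0%. A between-arm t test on the changes was significant in 5.1% two-sided, and in 2.5% in favour of robotic. Pattern and significant direct test favouring robotic occurred together in 2.4%. So where the pattern appeared, the direct test supported it in about 2.4/25.0, or one study in ten.

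**The case against.** The strongest reply is that the direct comparison is already planned. The sentence just before the paired tests provides a between-group t test, and section 9 ties a between-group difference to IPSS and IIEF by name. This stands. A reader might infer from the paired-test sentence that function is tested only within arms, or that a robotic advantage would be declared in up to a quarter of studies with no true difference. The protocol supports neither. It contains a between-arm test, and nowhere does it say that discordant paired tests establish superiority. The 25% is therefore the peak rate of a misleading pattern, not the error rate of a stated decision rule.

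It also stands that 25% is a ceiling. It needs paired tests with about 50% power, and the rate is below 5% when there is no decline or a large one.

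Two further replies stand in part. Change within each group does answer the first primary objective as worded, but a mean change with a confidence interval does so too, without a P value that invites comparison across arms. And the opening of 13.1 may concern descriptive summaries only, since 13.2 plainly compares groups; but 13.1 does not say so.

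Finally, the choice of visit and model can be left to a statistical analysis plan, which is not shown here. That answers a complaint about missing detail. It does not answer this point, because the protocol positively specifies significance tests of function within each arm and attaches baseline function to nothing else.

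**Conclusion.** The point holds as a weakness in how the analysis of function is fixed: the comparative conclusion on function is not assigned to the between-arm comparison, and within-arm tests at 0.05 stand beside it without being labelled descriptive. It should be corrected, but it does not show that the study lacks a valid comparison.

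The size depends on an assumed decline. For one tool at one visit, with equal true decline in both arms, it runs from under 1% to 25%, and lies between 14% and 25% for declines of 0.2 to 0.5 SD of change at 36 per arm. The calculation assumes independent arms, normally distributed changes and complete pairs. Six tools at three visits allow at most 6 × 3 = 18 such pairs, fewer where LARS is skipped because of a stoma; no overall rate across them is claimed, because their correlation is unknown. Confounding between the non-randomised arms is a separate matter, which comparing changes does not by itself resolve.

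**What to change.** - **Section 13.2:** state that the comparative conclusion on function rests on the between-arm difference in change from baseline (robotic minus laparoscopic), reported with its 95% CI.
- **Section 13.2:** replace the paired t tests by each arm's mean change from baseline with 95% CI, labelled descriptive and without P values. This still serves the first primary objective.
- **Section 13.1:** limit the statement about analysing cohorts separately to the descriptive summaries.

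The cost is wording in two sections. The data and the number of patients stay the same, and fewer tests are run. The downside is that the report loses the within-arm P values, which some readers will expect to see.

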7.2 Primary and Secondary Endpoints/Outcome Measures

Primary endpoints:

- 1. Assessment of functional outcomes by using validated questionnaires for bladder, bowel and sexual function pre-operatively, and after 3, 6 and 12 months.
 - International Prostatic Symptoms Score (IPSS) (male)
 - International Index of Erectile Function (IIEF) (male)
 - Female Sexual Function Index (FSFI) (female)
 - Kings Health questionnaire (female)
 - LARS-score (male/female) Not applicable at 3 and/or 6 months if the patient still has a stoma in situ at those respective follow-up moments
 - Vaizey score (male/female)
- 2. Measurement of stress response by taking blood samples at baseline and postoperative days 1, 3 and 5. Blood samples can be collected by anyone trained to do so and will be processed by an appropriately delegated member of the clinical team (including the research team). The following blood tests will be collected:
- White blood cell count (WBC)
- C-reactive protein (CRP)
- NLR (neutrophil lymphocyte ratio)
- IL-6
- IL-10
- TNFa
- MPO (neutrophil myeloperoxidase)

Some of the above blood tests (WBC, CRP, NLR, etc.) may be carried out as part of routine post-operative care. If these results are available, they can be used and additional sampling may not be required. Should these test results also be available for postoperative days 2 and 4, they can also be collected for use in this study, but this will be optional and no additional sampling will be done on these days.

Secondary outcomes:

- 1. Quality of life assessment using validated questionnaires (EORTC QLQ-C30/ CR29 and EQ-5D) at baseline, and after 3, 6 and 12 months.
- 2. Surgical outcomes, such as operative time, blood loss, stoma application, conversion, and intra-operative complications
- 3. Patient related outcomes:
 - a. Length of hospital stay
 - b. Opioid requirements and compliance with ERP
 - c. Worst vital signs post op
 - d. Worst pain scores
 - e. Time to flatus (in days) and return of bowel function
 - f. Early morbidity (up to 30-day postoperative complications, Clavien-Dindo Classification*)
 - g. Early mortality
 - h. Adverse events.
- 4. Optional: assessment of anorectal physiology after laparoscopic or robotic surgery in rectal cancer patients by using an anorectal manometry at baseline and after 1 year

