 - a. Assessment will be done in the outpatient clinic when patients come for their standard care preoperative and 12-month follow-up visit. The manometry will be performed by the clinical team using departmental equipment.

Grade I - Any deviation from normal post-operative course without the need of pharmacological or surgical intervention

Grade II - Requires pharmacological treatment

Grade III - Requires surgical, endoscopic or radiological intervention

Grade IV - Life threatening complication/ requiring ICU management

Grade V - Death of a patient

^{*}Clavien-Dindo classifications.36

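### Read literally, section 13.2's general rule of Fisher's exact test for categorical data would compare the ordered Clavien-Dindo grades as unordered categories

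*Protocol*

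**What the plan says.** Protocol section 7.2 lists among the secondary outcomes "Early morbidity (up to 30-day postoperative complications, Clavien-Dindo Classification", and its footnote sets out five grades of rising severity up to death, for example "Grade III - Requires surgical, endoscopic or radiological intervention". Section 6.3, objective 4, makes early morbidity one of the recovery outcomes to be compared between the surgical methods.

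Section 13.2, which covers the analysis of endpoints, contains two sentences that bear on the choice of test:

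- Fisher's "exact test will be used for categorical data", followed by a list of examples in brackets. The list is illustrative. T and N stage are ordered variables; the other examples are baseline or treatment descriptors.
- The comparison of blood cell counts, lymphocyte subsets and "clinic pathological variables will be performed using Chi-square tests, Kruskal–Wallis tests, and analysis of variance tests". White cell count and the neutrophil-lymphocyte ratio belong to the second primary endpoint, so Kruskal-Wallis is already named for some outcomes.

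Section 13.1 adds a descriptive rule: "Descriptive statistics will be provided for all discrete variables in the form of rates and proportions with 95% confidence intervals". No part of section 13 names Clavien-Dindo or morbidity, and no section reduces the grades to any complication or major complication.

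**The concern.** The grades form a severity scale. Section 4 links the size of the inflammatory response to the risk of postoperative complications and suggests that robotic dissection may reduce that response. The natural alternative is therefore fewer and milder complications, a move down the scale.

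An unordered test on a 2 x 6 table takes no account of the direction of that move. A shift from grade III to grade I counts like any other rearrangement of cells, and power is spread over five degrees of freedom. The P-value also comes with no effect estimate that uses the order. In a study of about 40 per arm, a real and consistent difference in morbidity would more often be reported as not significant than it need be.

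**Working it through.** **Inputs from the protocol.** Section 9: "Considering 80% power and a 0.05 (two-sided) significance level", and "a minimum of 36 patients were needed in each arm"; 10% loss to follow-up; 80 patients in total. Section 8.1: an approximately equal split between approaches.

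**The plan's own figure.** 36 / (1 - 0.10) = 40 per arm, and 2 x 40 = 80. The recruitment target is reproduced. It derives from the functional and cumulative scores; no power is stated for morbidity. Results below are given for 36 and 40 per arm.

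**Assumed inputs (not in the protocol).** Laparoscopic distributions over none/I/II/III/IV/V, in %:

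- 60/12/15/9/3/1
- 50/15/20/10/4/1
- 70/10/12/6/1.5/0.5
- 35/20/25/13/6/1

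The robotic distribution comes from multiplying each cumulative odds by a common odds ratio (OR) of 2, 3 or 4 towards milder grades. Example, first distribution, OR 2: the odds of no complication are 0.60/0.40 = 1.5; 1.5 x 2 = 3; 3/(1 + 3) = 0.75. Treating each cut in the same way gives about 75.0/8.7/9.3/4.9/1.5/0.5.

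**Tests compared, two-sided 0.05.**

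- Fisher (2 x 6, Freeman-Halton extension): P is the summed probability of all tables with the same margins that are no more probable than the one observed, by full enumeration.
- Rank test: z = (W - E)/√V, where W is the rank sum with midranks, E = n(N + 1)/2, and V is tie-corrected. With two groups, z² is the Kruskal-Wallis statistic.

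**Results.** 2,000 simulated studies per row. Relative loss = 1 - Fisher power / rank power, from unrounded powers.

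| None (assumed) | OR | Fisher, 36 | Rank, 36 | Loss | Fisher, 40 | Rank, 40 | Loss |
|---|---|---|---|---|---|---|---|
| 60% | 2 | 0.158 | 0.282 | 44% | 0.192 | 0.306 | 37% |
| 60% | 3 | 0.353 | 0.559 | 37% | 0.410 | 0.595 | 31% |
| 60% | 4 | 0.511 | 0.712 | 28% | 0.568 | 0.787 | 28% |
| 50% | 2 | 0.183 | 0.326 | 44% | 0.203 | 0.332 | 39% |
| 50% | 3 | 0.391 | 0.606 | 36% | 0.446 | 0.670 | 34% |
| 50% | 4 | 0.592 | 0.796 | 26% | 0.639 | 0.832 | 23% |
| 70% | 2 | 0.140 | 0.234 | 40% | 0.170 | 0.261 | 35% |
| 70% | 3 | 0.300 | 0.459 | 35% | 0.315 | 0.484 | 35% |
| 70% | 4 | 0.414 | 0.601 | 31% | 0.462 | 0.651 | 29% |
| 35% | 2 | 0.210 | 0.342 | 39% | 0.241 | 0.404 | 40% |
| 35% | 3 | 0.462 | 0.684 | 33% | 0.522 | 0.732 | 29% |
| 35% | 4 | 0.694 | 0.868 | 20% | 0.728 | 0.892 | 18% |

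With no true difference, rejection rates were 0.039 to 0.050 (Fisher) and 0.041 to 0.058 (rank), so the gain does not come from a lax test. The loss is 35-44% at OR 2, 29-37% at OR 3 and 18-31% at OR 4.

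**Binary alternative** (60% without complication, 36 per arm). Fisher 2 x 2 on any complication has power 0.198, 0.450 and 0.610 at OR 2, 3 and 4; on grade III or above, 0.055, 0.107 and 0.120. Both lie below the rank test.

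**Non-uniform shifts** (36 per arm, Fisher against rank):

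- Grade II falls in favour of no complication, other grades unchanged: 0.478 against 0.360.
- Minor grades fall, severe grades unchanged: 0.361 against 0.283.
- Movement only between grades I and II: 0.430 against 0.081.

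Here the ordering of the tests reverses.

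**The case against.** The strongest reply is that the protocol never says the grades will be tested this way. The Fisher sentence lists baseline and treatment variables, section 13 does not mention morbidity, and the choice of test for one secondary outcome is commonly left to a statistical analysis plan. Morbidity might be compared as a rate, in line with section 13.1, and a 2 x 2 Fisher test would then be suitable. Kruskal-Wallis, which is the needed test when there are two groups, is already named in 13.2.

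Much of this stands, and it rules out three stronger readings:

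- A reader might infer that every categorical variable is sent to Fisher's test. The text does not say so, and chi-square and Kruskal-Wallis appear in the same section.
- A reader might infer that at least a third of the power is lost. The loss falls to about a fifth for large effects and turns into a gain for Fisher under some non-uniform shifts. The main hypothesis in section 6.1 concerns stress response and function, so a uniform shift in grades is plausible but not predicted by the protocol.
- A reader might infer that the direction of any difference would stay hidden. The proportions with confidence intervals in section 13.1 would show it descriptively.

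What does not stand is that the point is mere silence. Section 13.2 sets a general rule, includes ordered variables in it, and leaves nothing that takes the grades out of it. If the grades were instead counted as clinicopathological variables, chi-square and Kruskal-Wallis would both be on offer without a choice between them. The binary reading appears nowhere in the text, and under a uniform shift it would still be less powerful than the rank test.

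**Conclusion.** The point holds in a limited form. Section 13.2 fixes a general rule that, followed literally, ignores the order of the Clavien-Dindo grades. Under a uniform downward shift the cost is 18% to 44% of the rank test's power, or 9 to 23 percentage points, at 36 to 40 per arm. This depends on assumed grade distributions, on odds ratios of 2 to 4 and on proportional odds; none of these is given in the protocol.

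Severity is low. The outcome is one item in a long secondary list and the study was not sized for it. At OR 2 even the rank test has power of only 0.23 to 0.40, so a moderate difference would usually be missed with either test. The change is still worth making because it costs almost nothing and settles the method before the data are seen.

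**What to change.** In section 13.2, limit Fisher's exact test to binary or unordered variables, and take T and N stage out of its examples to match. Then add a sentence such as:

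*The highest Clavien-Dindo grade within 30 days (none, I to V) will be compared between groups with the Wilcoxon rank-sum test, and the common odds ratio with its 95% confidence interval will be estimated from a proportional-odds model.*

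Keep the table of proportions by grade and group from section 13.1, so that a non-uniform pattern can be seen.

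The cost is a small edit to one section, with no new data; the rank-sum test is equivalent to the two-group Kruskal-Wallis test already named there. The downside is small: the common odds ratio assumes a roughly uniform shift and is less direct to read than a proportion.

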8. STUDY PARTICIPANTS

8.1 Study Setting

80 patients with rectal cancer with an elective indication for surgery will be recruited from Queen Alexandra Hospital in Portsmouth during an estimated 2-year period. This study will be observational, and all data will be collected prospectively.

The reason for choosing an observational study is that there is very little evidence on the subject. To run a randomised controlled trial at this moment, without evidence that there might be a trend towards a significant difference, would be a very costly decision with a possibly unjustified burden to the patients.

Since the unit performs over 100 rectal resections a year amongst 3 surgeons and there is an approximately equal split between robotic and laparoscopic cases, randomisation for creating equal groups will not be necessary in this stage.

If this observational study proves to be of significant value, we will proceed with a larger, multicentre randomised trial, taking these results into account in the designing stages.

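### Thirteen unranked primary measures are tested at an unadjusted 0.05, and the protocol gives no valid criterion for the 'similar' function limb or the joint main hypothesis

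*Protocol*

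**What the plan says.** The main hypothesis (section 6.1) is a joint claim: "Robotic surgery for rectal cancer results in a milder stress response and similar or better functional outcomes when compared to the laparoscopic approach".

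Section 7.2 gives two primary endpoint groups. The functional group uses "validated questionnaires for bladder, bowel and sexual function pre-operatively, and after 3, 6 and 12 months", with six instruments: IPSS and IIEF (men), FSFI and King's Health (women), LARS and Vaizey (both sexes). The blood group is "Measurement of stress response by taking blood samples at baseline and postoperative days 1, 3 and 5", with seven markers: WBC, CRP, NLR, IL-6, IL-10, TNFa and MPO. No instrument, marker, visit or day is ranked above another.

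Section 13.2 compares the two operations by a test of differences: "Student's t test will be used to analyse the differences between the two groups (L-TME vs. R-TME"). Comparisons of blood cell counts "will be performed using Chi-square tests, Kruskal–Wallis tests, and analysis of variance tests". After each of these paragraphs the same threshold appears: "A P-value of 0.05 will be considered statistically significant". There is no adjustment, no order of testing, no margin, and no statement of how the results combine to support section 6.1.

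Section 9 sizes the study only to detect differences (3.75 points on IPSS, 4.4 on IIEF, two-sided 0.05, 80% power). Section 8.1 says what may follow: "If this observational study proves to be of significant value, we will proceed with a larger, multicentre randomised trial".

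**The concern.** Two separate weaknesses meet here.

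First, many primary comparisons share one unadjusted threshold and none leads. Some nominally significant results are to be expected even if the operations do not differ, and nothing fixed in advance says which result counts.

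Second, section 6.1 claims that function is similar or better, and joins this by 'and' to a milder stress response. A t test of a difference can support 'better'. It cannot support 'similar', because a non-significant result may only mean that the study is small. The protocol gives no other criterion.

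At stake is what the study may conclude about function, and how its results are weighed when a randomised trial is considered.

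**Working it through.** **The plan's own figures.** Section 9 gives no SD, so its 35 per group can only be back-solved. By the two-sample t test at two-sided 0.05 and 80% power, 35 per group implies a standardised difference of 0.679, hence an IPSS SD of 3.75/0.679 = 5.52. The last step reproduces: 2 × 36 = 72, and 72/0.90 = 80.

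**Number of comparisons.**
- Functional: 6 instruments × 3 visits = 18.
- Blood: 7 markers × 3 days = 21.
- Together 39; with one time point per measure, 6 + 7 = 13.
- Not counted: the paired before-after t tests, and the optional blood results on days 2 and 4.

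**Chance of any false signal if nothing differs.**
- Expected false positives: 39 × 0.05 = 1.95, whatever the correlation.
- 39 independent tests: 1 − 0.95^39 = 0.865.
- 13 independent tests: 1 − 0.95^13 = 0.487.
- Simulation, 100,000 runs, assuming correlation of 0.3–0.7 between measures in a domain and 0.5–0.8 between visits, with blood uncorrelated with questionnaires and male-only with female-only instruments: 56–80% for 39 tests, 34–46% for 13.
- Simulation with one common correlation across all 39 tests: 74% at 0.3, 57% at 0.5, 37% at 0.7. The last is hard to reach, since the men's and women's instruments share no patients.

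**Why this is not the chance of falsely confirming section 6.1.** If the stress response does not differ, false support needs at least one stress result in favour of robotic surgery. Even if any one of the 21 sufficed, that chance is 1 − 0.975^21 = 0.41 if independent, and lower with correlation. The functional limb would have to be met as well.

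**What a t test says about 'similar'.** With 36 per arm and the implied SD, it is non-significant 19% of the time when the full planned difference exists and 70% of the time when half of it exists. IPSS is completed by men only. With 18–24 men per arm (assumed, 50–67% of 36) these become 37–49% and 79–83%.

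**Precision for IPSS.** The 95% CI half-width is t(0.975, 2n − 2) × SD × √(2/n), with SD 5.52:
- n = 18: 2.032 × 5.52 × 0.3333 = 3.74 points
- n = 22: 2.018 × 5.52 × 0.3015 = 3.36 points
- n = 24: 2.013 × 5.52 × 0.2887 = 3.21 points

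The SD matters. At n = 22 the half-width is 0.608 × SD: 3.04 at SD 5 and 4.26 at SD 7.

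**Power of a non-inferiority test on IPSS** (one-sided 0.025, no true difference, SD 5.52). The margins are assumptions, since the protocol gives none. The non-centrality parameter is margin/(SD × √(2/n)).
- Margin 3.75: n = 22 gives 3.75/(5.52 × 0.3015) = 2.25, power 60%; n = 23 gives 62%.
- Margin 2.8: n = 22 gives 2.8/(5.52 × 0.3015) = 1.68, power 38%; n = 23 gives 39%.

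**The case against.** The best defence is that multiplicity handling, a lead time point and a margin are often left to a statistical analysis plan. One may exist, and section 13.4 refers to one. That would answer a complaint about silence. It does not answer what the protocol itself fixes: an unadjusted 0.05, a difference test as the only between-group questionnaire test, and a hypothesis that this test cannot answer.

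A second defence is that the study is observational, single-centre and a step before a possible randomised trial. This softens the consequence. But the protocol also states a main hypothesis, 80% power and a significance threshold, so it does not present itself as purely exploratory.

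Several stronger readings are tempting and do not stand:
- A reader might infer that any one of 39 significant results makes the study positive. No such rule is stated, and the value needed to proceed to a randomised trial is not tied to a p-value.
- A reader might infer that p > 0.05 will be reported as 'similar'. The protocol never says so; it simply offers no other criterion.
- A reader might take 39 as the stated number of tests. Testing at every visit is an inference. Section 13.2 does not specify per-visit tests, and its blood paragraph names cell counts and lymphocyte subsets rather than cytokines. LARS is skipped at 3 or 6 months while a stoma remains, and no blood is drawn after early discharge.
- A reader might conclude that nothing in the main hypothesis can be tested. The individual tests for 'milder' and 'better' are valid at their nominal 0.05.

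**Conclusion.** The point holds in a limited form. The protocol has 13 primary measures without a lead and an unadjusted threshold, so an isolated significant result carries little weight. A false signal somewhere is likely if all 39 comparisons are made, unless the tests are strongly correlated throughout. With one time point per measure the chance is below one half, though still well above 5%.

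The firmer part does not depend on the count. The 'similar' limb and the joint claim in section 6.1 have no valid criterion. For illustration, at the back-solved SD and 18–24 men per arm, an observed IPSS difference of zero would barely exclude the 3.75 points used for planning. With an SD of 7 and 22 men per arm it would not exclude it. The number of men and the SD are assumptions, since the protocol gives neither.

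**What to change.** Before any outcome data are seen, amend sections 7.2 and 13.2 as follows.

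1. Name one lead functional endpoint at 12 months. One that both sexes complete (LARS or Vaizey) is preferable, because IPSS leaves women out of the functional test. Its SD and margin would need their own justification, as the protocol gives neither.
2. Name one lead stress marker on one day, for example CRP or IL-6 on day 3. Day 5 is less suitable, since patients discharged earlier have no sample.
3. State that both must succeed for section 6.1 to be supported. This both-must-succeed rule needs no split of alpha.
4. Judge 'similar or better' by the 95% CI for the functional difference against a justified margin stated in advance. If IPSS is used, the margin should be smaller than the 3.75 points planned as a difference to detect.
5. Report all other comparisons as estimates with 95% CIs, labelled exploratory.

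A Bonferroni correction is a poor alternative: at the implied effect and 36 per arm, power falls to 46% for 13 tests and 33% for 39.

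The change costs only wording, with no added visits or patients. The price is in the conclusions. Fewer results can be called significant, and non-inferiority may well not be shown: with 22–23 men per arm, power is about 60% at a 3.75-point IPSS margin and under 40% at 2.8, if there is truly no difference. The protocol should say that function is then reported as inconclusive, not as similar.
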